5.2.2.2 Dose Modifications for GM-CSF

GM-CSF can induce hematologic effects including variable increases in WBC and/or platelet counts, possibly leading to potential complications of excessive leukocytosis such as hyperviscosity, allergic reactions including anaphylaxis, fluid retention, and respiratory symptoms due to sequestration of granulocytes in pulmonary circulation. Monitoring of blood counts (CBC with differential) is recommended at least twice weekly during GM-CSF administration at standard doses. CBC with differential was checked twice weekly during GM-CSF induction cycles (Cycles 2 and 3) in Safety Cohort. As no increased leukocytosis was observed, weekly testing is performed in the Efficacy and Expansion Cohorts. Liver function and renal function should be monitored at least every 2 weeks on GM-CSF in patients at risk for renal or hepatic dysfunction. Body weight and hydration status should be carefully monitored during GM-CSF administration.

Table 4 Dose Modification Guidelines for GM-CSF-Related Adverse Events

Toxicity	Hold Treatment For Grade	Timing for Restarting*,** Treatment	Discontinue Subject
Leukocytosis	WBC 50,000-100,000/mm ³ and/or ANC > 20,000/mm ³	Hold drug and recheck within 3-7 days; if ANC < 10,000 mm ³ and WBC < 50,000 mm ³ and asymptomatic, re-start with 50% dose reduction (125 µg SQ daily) to complete 14 days; maintain dose reduction for next cycle(s)	If WBC count does not decrease to < 50,000/mm ³ within 3 weeks or recurs >100,000/mm ³ despite 50% dose reduction
	≥ 3 (WBC >100,000/mm ³) and/or hyperviscosity syndrome or complication	Permanently discontinue	Permanently discontinue
Thrombocytosis	Platelet count >500,000/mm ³	Hold drug and recheck within 3-7 days; if platelet count < 500,000/mm ³ and asymptomatic, then re-start with 50% dose reduction (125 µg SQ daily) to complete 14 days; maintain dose reduction for next cycle(s)	If platelet count does not decrease to < 500,000/mm ³ within 3 weeks or recurs >500,000/mm ³ despite 50% dose reduction
	>1,000,000/mm ³ and/or hyperviscosity syndrome or complication	Permanently discontinue	Permanently discontinue
Allergic reactions	3-4	Permanently discontinue	Permanently discontinue
Edema/fluid retention despite optimal supportive care (e.g. elevation, diuretics)	Moderate or severe (e.g. Grade ≥ 2 if obscuring normal contours or interfering with self-care)	Hold until edema recovers to Grade 0-1 or baseline, then re-start with 50% dose reduction (125 µg SQ daily) to complete 14 days; maintain dose reduction for next cycle(s)	If moderate or severe edema does not recover to Grade 0-1 or baseline within 3 weeks or if recurs despite dose reduction
All other drug-related toxicity ³ attributed to GM-CSF	3 or severe 2	Hold until toxicity resolves to Grade 0-1 or baseline, then re-start with 50% dose reduction (125 µg SQ daily) to complete 14 days; maintain dose reduction for next cycle(s)	Toxicity does not recover to Grade 0-1 or baseline within 3 weeks of last dose
	4	Permanently discontinue	Permanently discontinue

Note: Permanently discontinue for any severe AE that recurs or any life-threatening event.

* Dose interruptions or delays in start of a cycle for any reason (toxicity or non-toxicity) during Induction Phase (Cycles 1 and 2 in Efficacy Cohort (Part 2), Cycles 2 and 3 in Safety and Expansion Cohorts (Parts 1 and 3)) should be applied to both GM-CSF and pembrolizumab together so that both drugs are restarted on Day 1 of each cycle.

**Skipped or missed doses of GM-CSF during a cycle (e.g. due to logistical reasons, patient oversight, or other non-toxicity-related factors) may be made up at end of cycle daily up to 3 doses.

³ Patients with intolerable or persistent Grade <3 drug-related AE may hold study medication at physician discretion. Permanently discontinue study drug for persistent Grade 2 adverse reactions for which treatment with study drug has been held, that do not recover to Grade 0-1 within 3 weeks of the last dose.

Proprietary and Confidential

The information in this document is considered privileged and confidential, and may not be disclosed to others except to the extent necessary to obtain Institutional Review Board approval and informed consent, or as required by federal and state laws. Persons to whom this information is disclosed should be informed that this information is privileged and confidential and that it should not be further disclosed.

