5.2.2 Dose Modifications or Interruptions for Toxicity

Toxicity will be assessed according to the NCI CTCAE v4.0. Dose modifications, interruptions, and treatment discontinuation for one or both study drugs will be determined according to the system showing the greatest degree of toxicity and according to the treating investigator's assessment of toxicity attribution. Toxicity will be formally assessed at protocol-defined safety assessment time points well as by investigator review of weekly laboratory testing and, in the interim, by patient contact with the study team. General principles of toxicity management are listed below:

- Laboratory values should be rounded to one significant digit for grade determination according to standard rounding practice.
- Optimal supportive care should be provided for all clinically relevant toxicity.
 - See section 5.6 for guidance on supportive care/rescue medications for specific toxicities.
- Dose interruptions or delays in start of a cycle for any reason (toxicity or non-toxicity) during the Induction Phase (Cycles 1 and 2 in Efficacy Cohort, Cycles 2 and 3 in Safety and Expansion Cohorts) should be applied to both drugs together so that both drugs are restarted on Day 1 of each cycle.

- Doses of GM-CSF which are held during a cycle due to toxicity will not be re-administered.
- Doses of GM-CSF which are missed/skipped (e.g. due to logistical reasons, patient oversight, or other non-toxicity related factors) may be made up at end of cycle, daily for up to 3 doses. Missed/skipped doses >3 will not be re-administered.
- A patient will be removed from protocol therapy if pembrolizumab is permanently discontinued but may continue on pembrolizumab if GM-CSF is discontinued for toxicity before completing induction (2 cycles).
- For any toxicity (regardless of grade), despite optimal supportive care, that is felt by the treating investigator to represent a risk to the patient's safety, additional dose reduction, treatment delay, or treatment discontinuation is permitted at the discretion of the treating investigator.

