Trial Period:	Screening Phase ^p	Treatment Cycles ^a										End of Treatment	Post-Treatment		
		Cycle (C) 1			C2, C3			To be repeated on D1 each cycle beyond 8 cycles				Safety Follow-Up Visit ^b	Follow-Up Visits ^b	Survival Follow-Up	
Treatment Cycle/Title:	Main Study Screening	Day (D) 1	D8	D15	D1	D8	D15	C4 D1	C5 D1	C6 D1	C7 D1	C8 D1			
Scheduling Window (Days):	-28 to 1	± 3	± 3	± 3	± 3	± 3	± 3	± 3	± 3	± 3	± 3	± 3	Approx. 30 days (±14 days) post last treatment	Every 8 weeks ±28 days for 1 year post last treatment, then every 12 weeks ±28 days	Every 12 weeks ±28 days
m	Re-induction GM-CSF will be allowed case-by-case according to Section 7.1.5.1, between approximately months 6-12 or Cycles 8-16 on protocol therapy. In these cases, GM-CSF will be re-administered D1-14 for 2 cycles (which will be named “R” along with original cycle number, e.g. RC8 and RC9) along with GM-CSF Patient Diary/Injection Record (Appendix 11.2) which will be provided along with instructions before re-induction and collected on D1 of each cycle following the 2 re-induction cycles.														
n	CBCD must be checked day 1, day 5, day 8, and day 12 (±3 days) during Cycles 2 and 3 (induction GM-CSF) of Safety Cohort.														
o	On Day 15 of Cycles 1, 2, and 3, the clinic visit for physical examination, vitals, and weight check may be omitted provided there are no clinically-significant AE requiring follow up at Day 8 visit at discretion of treating investigator. If clinic visit is omitted, telephone encounters must be performed to review AE and concomitant medications at these time points and documented in electronic medical record by treating investigator. Appropriate follow up for any new symptomatic or laboratory AE must be coordinated as needed based upon this encounter. Research PBMC sample may be omitted in cases which do not require clinic visit on Cycle 1, Day 15.														
p	Screening tests and procedures do not need to be repeated on Cycle 1, Day 1 if performed within 3 days.														

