6.4 Expansion Cohort Flow Chart

Trial Period:	Screening Phase ^p	Treatment Cycles ^a										End of Treatment	Post-Treatment		
Treatment Cycle/Title:	Main Study Screening	Cycle (C) 1			C2, C3			To be repeated on D1 each cycle beyond 8 cycles					Safety Follow-Up Visit ^b	Follow-Up Visits ^b	Survival Follow-Up
		Day (D) 1	D8	D15	D1	D8	D15	C4 D1	C5 D1	C6 D1	C7 D1	C8 D1			
Scheduling Window (Days):	-28 to 1	± 3	± 3	± 3	± 3	± 3	± 3	± 3	± 3	± 3	± 3	± 3	Approx. 30 days (±14 days) post last treatment	Every 8 weeks ±28 days for 1 year post last treatment then every 12 weeks ±28 days	Every 12 weeks ±28 days
Administrative Procedures															
Informed Consent	X														
Inclusion/Exclusion Criteria	X														
Demographics and Medical History	X														
Prior and Concomitant Medication Review	X	X	X	X	X	X	X	X	X	X	X	X			
Pembrolizumab Administration ^a		X			X			X	X	X	X	X			
GM-CSF Administration Days 1-14 ^{a,m}					D1-14 ^m										
GM-CSF Patient Diary/Injection Record ^{c,m} (Appendix 11.2)					X ^m			X ^m							
Post-Study Anticancer Therapy Status												X	X	X	
Survival Status												X	X	X	
Clinical Procedures/Assessments															
Review Adverse Events	X	X	X	X	X	X	X	X	X	X	X	X ^d			
Full Physical Examination	X	X	X		X	X		X	X	X	X	X			
Vital Signs and Weight	X	X	X		X	X		X	X	X	X	X			
ECOG Performance Status (Appendix 11.4)	X	X	X		X	X		X	X	X	X	X			
Child Pugh Score (Appendix 11.5)	X														
Laboratory Procedures/Assessments: analysis performed by LOCAL laboratory															
Pregnancy Test – Urine or Serum β -HCG ^e	X	X			X			X	X	X	X	X			
PT/INR	X	X			X			X	X	X	X	X	X	X	

UCSF Helen Diller Family Comprehensive Cancer Center

Version date: 10/01/2019

Protocol CC#: 154524

Trial Period:	Screening Phase ^p	Treatment Cycles ^a										End of Treatment	Post-Treatment							
Treatment Cycle/Title:	Main Study Screening	Cycle (C) 1			C2, C3			To be repeated on D1 each cycle beyond 8 cycles					Safety Follow-Up Visit ^b	Follow-Up Visits ^b	Survival Follow-Up					
		Day (D) 1	D8	D15	D1	D8	D15	C4 D1	C5 D1	C6 D1	C7 D1	C8 D1								
Scheduling Window (Days):	-28 to 1	± 3	± 3	± 3	± 3	± 3	± 3	± 3	± 3	± 3	± 3	± 3	Approx. 30 days (±14 days) post last treatment	Every 8 weeks ±28 days for 1 year post last treatment then every 12 weeks ±28 days	Every 12 weeks ±28 days					
aPTT	X																			
CBC with Differential	X	X	X		X	X		X	X	X	X	X	X							
Comprehensive Serum Chemistry Panel ^f	X	X	X		X	X		X	X	X	X	X	X							

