Urinalysis ^g	X			Every 8 weeks from C1D1 ± 14 days								X								
T3, FT4 and TSH ^g	X			Every 8 weeks from C1D1 ± 14 days								X								
Efficacy Measurements																				
Tumor Imaging ^h	X		Every 8 weeks from C1D1 (±7 days for first 6 months of treatment, ± 14 days after 6 months until end of treatment) ^h									X ^h								
Confirmation of RECIST 1.1-Measurable ^g	X																			
Confirmation of Biopsy-Accessible ^g	X																			
CA 19-9 Tumor Marker ⁱ	X		Every 8 weeks from C1D1 ± 14 days								X ⁱ									
Archival Tissue Collection/Correlative Studies Blood (Appendix 11.6)																				
Archival Tumor Tissue Collection ^j	X ^j												X ^j	X ^j						
On-Treatment Tumor Research Biopsy ^r				C1D 15			C3D 15 after scans													
PBMC Blood Collection ^k	X	X	X		X	X	Every 8 weeks ± 14 days through C9D1					X	X ^k							
^a	Cycle length is 21 days, ±3 days. Pembrolizumab is administered IV Q21 days ±3 up to 24 months or 35 cycles (Sections 5.2, 5.8, 7.1.5.2). GM-CSF is administered days 1-14 Q21 days, ±3 days for induction Cycles 2 and 3 only with option for re-induction in cases meeting criteria in Section 7.1.5.1; Dayday 1 and subsequent doses are self-is administered after self-injection teaching by infusion center RN or another qualified medical provider each cycle.																			
^b	A mandatory Safety Follow-Up Visit should be conducted approximately 30 days after the last dose of trial treatment or before the initiation of a new anti-cancer treatment, whichever comes first. All AEs that occur prior to the Safety Follow-Up Visit should be recorded. Though the Safety Follow-Up Visit and assessments should be performed at UCSF when possible, safety follow up assessments (including administrative, clinical,																			

Trial Period:	Screening Phase ^p	Treatment Cycles ^a										End of Treatment	Post-Treatment		
Treatment Cycle/Title:	Main Study Screening	Cycle (C) 1			C2, C3			To be repeated on D1 each cycle beyond 8 cycles					Safety Follow-Up Visit ^b	Follow-Up Visits ^b	Survival Follow-Up
		Day (D) 1	D8	D15	D1	D8	D15	C4 D1	C5 D1	C6 D1	C7 D1	C8 D1			
Scheduling Window (Days):	-28 to 1	± 3	± 3	± 3	± 3	± 3	± 3	± 3	± 3	± 3	± 3	± 3	Approx. 30 days (±14 days) post last treatment	Every 8 weeks ±28 days for 1 year post last treatment then every 12 weeks ±28 days	Every 12 weeks ±28 days

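### The text says blood counts are weekly on GM-CSF, but two flow charts schedule none between Day 8 and the next cycle's Day 1

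*Combined protocol and SAP*

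**What the plan says.** Section 5.2.2.2 states that blood-count monitoring "is recommended at least twice weekly during GM-CSF administration at standard doses". It reports that the Safety Cohort was checked twice weekly and that, because no increased leukocytosis was seen, "weekly testing is performed in the Efficacy and Expansion Cohorts". Section 5.2.2 says toxicity is also assessed by "investigator review of weekly laboratory testing".

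For the Expansion Cohort, footnote a of the 6.4 chart says "GM-CSF is administered days 1-14 Q21 days, ±3 days for induction Cycles 2 and 3 only". In the same chart, the "CBC with Differential" row is marked at Day 1 and Day 8 of Cycles 2 and 3. A Day 15 column exists, but the cell is blank. The Efficacy chart (6.2) has a Day 15 visit in Cycle 1 only; in Cycle 2, that cohort's second GM-CSF cycle, counts fall on Day 1 and Day 8. In the Safety chart (6.1), footnote n says "CBCD must be checked day 1, day 5, day 8, and day 12" in Cycles 2 and 3, and the row is also marked at Day 15.

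The GM-CSF dose-modification table (Table 4 in 5.2.2.2) sets hold, half-dose and stop limits on WBC, ANC and platelets. It carries a dose reduction forward into later cycles.

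**The concern.** Section 7.1 presents the flow charts as the summary of what is done at each visit, so a coordinator will order tests from the chart. In the Expansion Cohort that does not give a count every seven days, although the text says testing is weekly. No footnote to 6.4 adds the missing count.

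Two things are at stake. First, several limits in the GM-CSF table depend on laboratory values. A rise that begins after the Day 8 sample and settles before the next Day 1 would be seen by no scheduled test, and could not inform the reduction or discontinuation decision for the second induction cycle. Second, safety is a key secondary objective and laboratory assessments are among its endpoints (8.3.2). Count-defined events are recorded only when a count is taken.

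**Working it through.** **Inputs.** GM-CSF is given on Days 1-14 of a 21-day cycle. The visit window is ±3 days. Day 1 assessments precede the Day 1 dose (5.2.3.2). Up to three missed doses may be made up at the end of the cycle (5.2.2).

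**Is the blank cell real?** The 6.4 CBC row has 13 cells for the 13 columns from Screening to the Safety Follow-Up Visit. The empty ones are Day 15 of Cycle 1 and Day 15 of Cycles 2-3. The chemistry row has the same pattern, so a layout slip is unlikely.

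**Scheduled counts in a GM-CSF cycle (nominal days; Day 22 is the next Day 1).**

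| Chart | GM-CSF cycles | CBC days | Intervals (days) |
|---|---|---|---|
| 6.1 Safety | 2, 3 | 1, 5, 8, 12, 15, 22 | 4, 3, 4, 3, 7 |
| 6.2 Efficacy | 1 | 1, 8, 15, 22 | 7, 7, 7 |
| 6.2 Efficacy | 2 | 1, 8, 22 | 7, 14 |
| 6.4 Expansion | 2, 3 | 1, 8, 22 | 7, 14 |
| Re-induction, all three charts | two within 8-16 | 1, 22 | 21 |

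A seven-day interval is reproduced only for Cycle 1 of the Efficacy chart. It is not reproduced for Cycle 2 of that chart or for either Expansion induction cycle.

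**The long gap.**
- Nominal: 22 − 8 = 14 days.
- Shortest with windows: (22 − 3) − (8 + 3) = 8 days.
- Longest with windows: (22 + 3) − (8 − 3) = 20 days.
- Last planned dose to next count: 22 − 14 = 8 days.

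**What the Day 8 count can still do.** Taken on Day 8, it precedes up to 14 − 8 + 1 = 7 doses. Taken on Day 11, the end of its window, it precedes 14 − 11 + 1 = 4. It can therefore trigger a hold or stop in the second dosing week, and a hold for leukocytosis or thrombocytosis brings its own recheck in 3-7 days.

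**What a Day 15 count would add.** Nominally it falls 15 − 14 = 1 day after the last planned dose. Its window is Days 12-18, so it could fall during dosing. It could also do so if make-up doses directly follow Day 14, since 14 + 3 = 17. At its nominal day it adds no check between Day 8 and Day 14, but it splits the 14-day gap into 7 and 7.

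**Re-induction.** From Cycle 4 on, all three charts schedule Day 1 visits only. Footnote m of each chart allows GM-CSF on Days 1-14 for two further cycles and adds no CBC; in 6.2 it adds a PTT on Day 1.

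**Number of courses.** Expansion Cohort: 15 × 2 = 30 if every patient completes both cycles. Efficacy Cohort: 18 × 1 = 18, with enrollment already complete.

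**The case against.** The best reply is that *weekly* means once per dosing week. The Safety Cohort's twice-weekly testing corresponds to Days 1, 5, 8 and 12, two counts in each of two dosing weeks. By the same convention, weekly would be Days 1 and 8, which is what 6.4 schedules. Day 15 lies after the last planned dose. This reading is plausible but does not settle the matter: the Safety chart also marks Day 15 in its GM-CSF cycles, and the Efficacy chart marks it in Cycle 1 but has no such visit in Cycle 2. Nor does it explain re-induction, where no count is scheduled after Day 1.

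It is also fair that the phrase in 5.2.2 is general. It cannot be literal for the whole trial, because every chart moves to one count per three-week cycle from Cycle 4. It supports the point only weakly.

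A reader might go further and infer that the dose limits cannot act in the second week of dosing, or that the rules depend on counts alone. The documents do not support either:
- The Day 8 result governs Days 8-14.
- The table also has triggers based on hyperviscosity or other complications, allergic reaction and edema.
- Section 7.1 allows unscheduled tests.
- Footnote o of 6.4 requires a telephone adverse-event review if the Day 15 visit is omitted.

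A reader might also object to relaxing the frequency on the strength of nine Safety Cohort patients. That is a disclosed choice with a stated reason, and is separate from whether text and chart agree. Likewise, the difference between three counts on dosing days in the Safety Cohort (Days 5, 8, 12) and one in the Expansion Cohort comes mainly from that choice; a nominal Day 15 count would not change it.

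**Conclusion.** The mismatch stands in limited form. Section 5.2.2.2 and the charts do not state one CBC schedule for GM-CSF. On a calendar-week reading, the charts miss one count in each Expansion induction cycle and in Cycle 2 of the Efficacy Cohort. On a dosing-week reading, the induction charts comply but the re-induction courses do not.

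The consequence is a detection gap, not a failure of the dose rules. A count abnormality first arising after the Day 8 sample has no scheduled detection for nominally 14 days (8 to 20 with windows), ending about 8 days after the last planned dose. It may go unrecorded and may not inform the rules that carry into the next cycle. How often this happens cannot be estimated from the documents.

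The primary endpoint, ORR, is not affected. Section 8.6.2.1 plans safety summaries over all subjects and by anatomic subtype, not by cohort, so the effect on reporting is that pooled frequencies of leukocytosis and thrombocytosis would mix different ascertainment schedules. The conclusion assumes nominal visit days, no unscheduled counts and an intact CBC row in 6.4. It takes no view on which monitoring frequency is right.

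**What to change.** Reconcile 5.2.2, 5.2.2.2, the CBC rows of 6.2 and 6.4, and footnote m on re-induction, so that text and charts state one CBC schedule during GM-CSF. The sponsor must decide which governs. Naming the cycle days in the text would remove the ambiguity in *weekly*.

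For the Efficacy Cohort, initial induction followed enrollment that closed in September 2017, so a correction there serves the record and any re-induction course still to be given.

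In the safety summary, report leukocytosis and thrombocytosis by cohort, with the count schedule each cohort actually had, including any unscheduled counts.

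The cost is a text and flow-chart correction in the next amendment. If the text governs on the calendar-week reading, it also means one routine CBC per Expansion induction cycle; in Cycle 3 this falls at about the time of the Day 15 research biopsy. If the charts govern, there is no added testing for the two induction cycles.

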5.2.2.3 Dose Interruptions or Delays for Reasons Other than Toxicity

Dosing interruptions are permitted in the case of medical / surgical events or logistical reasons not related to study therapy (e.g., elective surgery, unrelated medical events, administrative reasons, patient vacation, and/or holidays). Subjects should be placed back on study therapy within approximately 3 weeks of the scheduled interruption, unless otherwise discussed with the Study Chair. The reason for interruption should be documented in the patient's study record.

5.2.3 Dose Preparation and Timing

GM-CSF and pembrolizumab doses will be prepared by Investigational Pharmacist according to FDA package insert instructions for each drug.

All trial treatments will be administered on an outpatient basis.

5.2.3.1 Timing of Pembrolizumab Administration

Pembrolizumab will be administered on Day 1 of each 21-day cycle after all procedures/assessments have been completed as detailed on the Trial Flow Chart (Section 6.0). Trial treatment may be adjusted up to 3 days before or after the scheduled Day 1 of each cycle due to administrative or other logistical reasons such as holidays/schedule conflicts.

Pembrolizumab 200 mg will be administered as a 30 minute IV infusion on Day 1 of each cycle, every 3 weeks. Sites should make every effort to target infusion timing to be as close to 30 minutes as possible. However, given the variability of infusion pumps from site to site, a window of approximately -5 minutes and +10 minutes is permitted (i.e., approximate infusion time is 30 minutes: -5 min/+10 min).

5.2.3.2 Timing of GM-CSF Administration

GM-CSF will be administered starting Day 1 of each induction cycle after all procedures/assessments have been completed as detailed on the Trial Flow Chart (Section 6.0), then continued daily through Day 14 (Days 1-14 Q21 days, in Cycles 2 and 3 for the Safety Cohort (n=9) and Expansion Cohort (n=15). GM-CSF induction is administered in Cycles 1 and 2 in the Efficacy Cohort based upon acceptable safety in the Safety Cohort. Trial treatment may be adjusted up to 3 days before or after the scheduled Day 1 of each cycle due to administrative or other logistical reasons such as holidays/schedule conflicts.

GM-CSF 250 µg will be administered as a SC injection days 1-14 every 3 weeks during the Induction Phase (Cycles 1 and 2). Day 1 injection each cycle will be self-administered (after self-injection teaching by an infusion center RN or another qualified medical provider), after pembrolizumab infusion with additional self-injection training/re-training as needed at each GM-CSF time point. Subsequent injections will be self-administered by patient or family member/friend. Effort should be made to administer GM-CSF at approximately the same time each day (\pm 3 hours from Day 1 dosing time).

Missed/skipped GM-CSF doses (e.g. due to logistical reasons, patient oversight, or other non-toxicity-related factors) may be made up at end of cycle daily up to 3 doses.

